11.3.8 Source Documents

The investigator is to maintain a list of appropriately qualified persons to whom he/she has delegated study duties. All persons authorized to make entries and/or corrections on eCRFs will be included on the Amgen Delegation of Authority Form.

Source documents provide evidence for the existence of the subject and substantiate the integrity of the data collected. Source documents are filed at the investigator's site.

Source documents are original documents, data, and records from which the subject's eCRF data are obtained. These include but are not limited to hospital records, clinical and office charts, laboratory and pharmacy records, diaries, microfiches, radiographs, and correspondence. Source documents may also include data captured in the Interactive Response Technology (IRT) system (if used, such as subject ID and randomization number) and eCRF entries if the eCRF is the site of the original recording (ie, there is no other written or electronic record of data, such as paper questionnaires for a clinical outcome assessment).

Data reported on the eCRF or entered in the eCRF that are transcribed from source documents must be consistent with the source documents or the discrepancies must be explained. The investigator may need to request previous medical records or transfer records, depending on the study. Also, current medical records must be available.

The investigator and study staff are responsible for maintaining a comprehensive and centralized filing system of all study-related (essential) documentation, suitable for inspection at any time by representatives from Amgen and/or applicable regulatory authorities.

Elements to include:

- Subject files containing completed eCRFs, ICFs, and subject identification list
- Study files containing the protocol with all amendments, investigator's Brochure, copies of prestudy documentation, and all correspondence to and from the [IRB/IEC] and Amgen
- Investigational product-related correspondence including [Proof of Receipts, Investigational Product Accountability Record(s), Return of Investigational Product for Destruction Form(s), Final Investigational Product Reconciliation Statement, as applicable
- Non-investigational product(s), and/or medical device(s) or combination product(s) documentation, as applicable

Retention of study documents will be governed by the Clinical Trial Agreement.

11.3.9 Study and Site Closure

Amgen or its designee may stop the study or study site participation in the study for medical, safety, regulatory, administrative, or other reasons consistent with applicable laws, regulations, and GCP.

Both Amgen and the investigator reserve the right to terminate the investigator's participation in the study according to the Clinical Trial Agreement. The investigator is to notify the IRB/IEC in writing of the study's completion or early termination and send a copy of the notification to Amgen.

Subjects may be eligible for continued treatment with Amgen investigational product(s) by an extension protocol or as provided for by the local country's regulatory mechanism. However, Amgen reserves the unilateral right, at its sole discretion, to determine whether to supply Amgen investigational product(s) and by what mechanism, after termination of the study and before the product(s) is/are available commercially.

11.3.10 Compensation

Any arrangements for compensation to subjects for injury or illness that arises in the study are described in the Compensation for Injury section of the Informed Consent that is available as a separate document.

11.4 Appendix 4. Safety Events: Definitions and Procedures for Recording, Evaluating, Follow-up and Reporting

11.4.1 Definition of Adverse Event

Adverse Event Definition

- An adverse event is any untoward medical occurrence in a clinical study subject irrespective of a causal relationship with the study treatment.
- Note: An adverse event can therefore be any unfavorable and unintended sign (including an abnormal laboratory finding), symptom, or disease (new or exacerbated) temporally associated with the use of a treatment, combination product, medical device or procedure.
- Note: Treatment-emergent adverse events will be defined in the statistical analysis plan

Events Meeting the Adverse Event Definition

- Any abnormal laboratory test results (hematology, clinical chemistry, or urinalysis) or other safety assessments (eg, electrocardiogram, radiological scans, vital signs measurements), including those that worsen from baseline, that are considered clinically significant in the medical and scientific judgment of the investigator (ie, not related to progression of underlying disease).
- Exacerbation of a chronic or intermittent pre-existing condition including either an increase in frequency and/or intensity of the condition.
- New conditions detected or diagnosed after study treatment administration even though it may have been present before the start of the study.
- Signs, symptoms, or the clinical sequelae of a suspected drug-drug interaction.
- Signs, symptoms, or the clinical sequelae of a suspected overdose of either study treatment or a concomitant medication. Overdose per se will not be reported as an adverse event/serious adverse event unless it is an intentional overdose taken with possible suicidal/self-harming intent. Such overdoses are to be reported regardless of sequelae.
- “Lack of efficacy” or “failure of expected pharmacological action” per se will not be reported as an adverse event or serious adverse event. Such instances will be captured in the efficacy assessments. However, the signs, symptoms, and/or clinical sequelae resulting from lack of efficacy will be reported as adverse event or serious adverse event if they fulfill the definition of an adverse event or serious adverse event.

Events NOT Meeting the Adverse Event Definition

- Medical or surgical procedure (eg, endoscopy, appendectomy): the condition that leads to the procedure is the adverse event.
- Situations in which an untoward medical occurrence did not occur (social and/or convenience admission to a hospital).

- Anticipated day-to-day fluctuations of pre-existing disease(s) or condition(s) present or detected at the start of the study that do not worsen.

11.4.2 Definition of Serious Adverse Event

A Serious Adverse Event is defined as any untoward medical occurrence that, meets at least 1 of the following serious criteria:

Results in death (fatal)

Immediately life-threatening The term “life-threatening” in the definition of “serious” refers to an event in which the subject was at risk of death at the time of the event. It does not refer to an event, which hypothetically might have caused death, if it were more severe.

Requires in-patient hospitalization or prolongation of existing hospitalization In general, hospitalization signifies that the subject has been detained (usually involving at least an overnight stay) at the hospital or emergency ward for observation and/or treatment that would not have been appropriate in the physician’s office or outpatient setting. Complications that occur during hospitalization are an adverse event. If a complication prolongs hospitalization or fulfills any other serious criteria, the event is serious. When in doubt as to whether “hospitalization” occurred or was necessary, the adverse event is to be considered serious. Hospitalization for elective treatment of a pre-existing condition that did not worsen from baseline is not considered an adverse event.

Results in persistent or significant disability/incapacity The term disability means a substantial disruption of a person’s ability to conduct normal life functions. This definition is not intended to include experiences of relatively minor medical significance such as uncomplicated headache, nausea, vomiting, diarrhea, influenza, and accidental trauma (eg, sprained ankle) which may interfere with or prevent everyday life functions but do not constitute a substantial disruption.

Is a congenital anomaly/birth defect


Other medically important serious event Medical or scientific judgment is to be exercised in deciding whether serious adverse event reporting is appropriate in other situations such as important medical events that may not be immediately life-threatening or result in death or hospitalization but may jeopardize the subject or may require medical or surgical intervention to prevent 1 of the other outcomes listed in the above definition. These events are typically to be considered serious. Examples of such events include invasive or malignant cancers, intensive treatment in an emergency room or at home for allergic bronchospasm, blood dyscrasias or convulsions that do not result in hospitalization, or development of drug dependency or drug abuse.

11.4.3 Definition of Adverse Device Effect

The detection and documentation procedures for adverse device effects described in this protocol apply to all Amgen medical devices provided for use in the study (see Section 6.1.3 for the list of Amgen medical devices).

Adverse Device Effect Definition

An adverse device effect is any adverse event related to the use of a combination product or medical device. Adverse device effects include adverse events resulting from insufficient or inadequate instructions for use, adverse events resulting from any malfunction of the device, or adverse events resulting from use error or from intentional misuse of the device.

A combination product is a product composed of any combination of a drug, a device, and a biological product. Each drug, device, and biological product included in a combination product is referred to as a “constituent part” of the combination product.

11.4.4 Recording Adverse Events and Serious Adverse Events

Adverse Event and Serious Adverse Event Recording

- When an adverse event or serious adverse event occurs, it is the responsibility of the investigator to review all documentation (eg, hospital progress notes, laboratory, and diagnostics reports) related to the event.
- The investigator will then record all relevant adverse event/serious adverse event information in the Event electronic case report form (eCRF).
- The investigator must assign the following adverse event attributes:
 - Adverse event diagnosis or syndrome(s), if known (if not known, signs or symptoms);
 - Dates of onset and resolution (if resolved);
 - Did the event start prior to first dose of investigational product, other protocol-required therapies;
 - Severity (or toxicity defined below);
 - Assessment of relatedness to investigational product(s), other protocol-required therapies, devices, and/or study-mandated activity and/or procedures;
 - Action taken; and
 - Outcome of event
- If the severity of an adverse event changes from the date of onset to the date of resolution, record as a single event with the worst severity on the Events eCRF
- It is not acceptable for the investigator to send photocopies of the subject's medical records to the sponsor in lieu of completion of the Events eCRF page.
- If specifically requested, the investigator may need to provide additional follow-up information, such as discharge summaries, medical records, or extracts from the medical records. In this case, all subject identifiers, with the exception of the subject number, will be blinded on the copies of the medical records before submission to Amgen.
- The investigator will attempt to establish a diagnosis of the event based on signs, symptoms, and/or other clinical information. In such cases, the diagnosis (not the

individual signs/symptoms) will be documented as the adverse event/serious adverse event.

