8.2.3.1 Adverse Events and Serious Adverse Events

8.2.3.1.1 Time Period and Frequency for Collecting and Reporting Safety Event Information

8.2.3.1.1.1 Adverse Events

The adverse event grading scale to be used for this study will be the Common Terminology Criteria for Adverse Events (CTCAE) v4.03 and is described in Section [11.4](#).

The investigator is responsible for ensuring that all adverse events observed by the investigator or reported by the subject that occur after the first dose of investigational product through the end of study are reported using the Events eCRF.

8.2.3.1.1.2 Serious Adverse Events

The investigator is responsible for ensuring that all serious adverse events observed by the investigator or reported by the subject that occur after signing of the informed consent through end of study are reported using the Events eCRF.

All serious adverse events will be collected, recorded and reported to the sponsor or designee within 24 hours, **of the investigator's awareness of the event**, as indicated in Section [11.4](#). The investigator will submit any updated serious adverse event data to the sponsor within 24 hours of it being available.

The criteria for grade 4 in the CTCAE grading scale differs from the regulatory criteria for serious adverse events. It is left to the investigator's judgment to report these grade 4 abnormalities as serious adverse events. **For any adverse event that applies to this situation, comprehensive documentation of the event's severity must be recorded in the subject medical records.**

8.2.3.1.1.3 Serious Adverse Events After the Protocol-required Reporting Period

After End of Study, there is no requirement to **actively** monitor study subjects **after the study has ended with regards to study subjects treated by the investigator. However, if the investigator becomes aware of serious adverse events suspected to be related to investigational product, then these serious adverse events will be reported to Amgen within 24 hours following the investigator's awareness of the event.**

Per local requirements in some countries, investigators are required to report serious adverse events that they become aware of after end of study. If serious adverse events are reported, the investigator is to report them to Amgen within 24 hours following the investigator's knowledge of the event.

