- The investigator is obligated to perform or arrange for the conduct of supplemental measurements and/or evaluations as medically indicated or as requested by Amgen to elucidate the nature and/or causality of the adverse event or serious adverse event as fully as possible. This may include additional laboratory tests or investigations, histopathological examinations, or consultation with other health care professionals.
- If a subject is permanently withdrawn from protocol-required therapies because of a serious adverse event, this information must be submitted to Amgen.
- If a subject dies during participation in the study or during a recognized follow-up period, the investigator will provide Amgen with a copy of any post-mortem findings including histopathology.
- New or updated information will be recorded in the originally completed Event eCRF.
- The investigator will submit any updated serious adverse event data to Amgen within 24 hours of receipt of the information.

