Date Started* – Enter date the adverse event first started (not the date on which the event met serious criteria) rather than the date of diagnosis or hospitalization. **This is a mandatory field.**

Date Ended – Enter date the adverse event ended and not the date when the event no longer met serious criteria. If the event has not ended at the time of the initial report, a follow-up report should be completed when the end date is known. If the event is fatal, enter the date of death as the end date.

If event occurred before the first dose of Investigational Product (IP)/drug under study, add a check mark in the corresponding box.

Is event serious?* – Indicate Yes or No. **This is a mandatory field.**

Serious Criteria Code* – **This is a mandatory field for serious events.** Enter all reasons why the reported event has met serious criteria:

- Immediately life-threatening – Use only if the subject was at immediate risk of death from the event as it occurred. Emergency treatment is often required to sustain life in this situation.
- If the investigator decides an event should be reported in an expedited manner, but it does not meet other serious criteria, "Other Medically Important Serious Event" may be the appropriate serious criterion.

Relationship to IP – The Investigator must determine and enter the relationship of the event to the IP at the time the event is initially reported. **This is a mandatory field.**

Relationship to Amgen device* – The Investigator must determine and enter the relationship of the event to the Amgen device (e.g. prefilled syringe, auto-injector) at the time the event is initially reported. **If the study involves an Amgen device, this is a mandatory field. This question does not apply to non-Amgen devices used in the study (e.g. heating pads, infusion pumps)**

Outcome of Event* – Enter the code for the outcome of the event at the time the form is completed. **This is a mandatory field.**

- Resolved – End date is known
- Not resolved / Unknown – End date is unknown
- Fatal – Event led to death

If event is related to a study procedure, such as a biopsy, radiotherapy or withdrawal of a current drug treatment during a wash-out period, add a check mark to the corresponding box. This does not include relationship to IP or concomitant medication – only diagnostic tests or activities mandated by the protocol.

4. Hospitalization

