5.1.3 Safety Endpoints

Treatment-emergent Adverse Event (TEAE)

An event categorized as “Adverse Event” on the Events eCRF starting on or after first dose of investigational product, as determined by “Did event start before first dose of investigational product” equal to “No” or missing, and up to the End of Study date.

Serious Treatment-emergent Adverse Event

A treatment-emergent adverse event with the indicator flag “Serious” equal to “Yes” on the Events eCRF.

Treatment-emergent Adverse Device Effect

A treatment-emergent adverse event with the indicator flag “Is there a reasonable possibility that the event may have been caused by the investigational device” equal to “Yes” on the Events eCRF.

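### A serious event that starts before first dose and worsens on erenumab can never count as treatment-emergent, and the onset date of a non-serious exacerbation is left undefined

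*Protocol*

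**What the plan says.** Five provisions meet on this point.

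- **Change in severity (Protocol 11.4.4).** An event that changes grade stays on one row: if its severity "changes from the date of onset to the date of resolution, record as a single event with the worst severity on the Events eCRF". Each row has one onset date and one timing item: "Did the event start prior to first dose of investigational product, other protocol-required therapies". No listed attribute captures when the event worsened or what grade it had at first dose.
- **Updates (Protocol 11.4.5).** "New or updated information will be recorded in the originally completed Event eCRF".
- **Collection windows (Protocol 8.2.3.1.1).** Non-serious adverse events are collected only after first dose. Serious adverse events (SAEs) are collected earlier, namely those "that occur after signing of the informed consent through end of study are reported using the Events eCRF".
- **What counts as an adverse event (Protocol 11.4.1).** The list includes "Exacerbation of a chronic or intermittent pre-existing condition including either an increase in frequency and/or intensity of the condition". Day-to-day fluctuation is excluded only where the condition does not worsen. The section leaves the definition of treatment-emergent to the SAP.
- **TEAE (SAP 5.1.3).** This is an adverse event "starting on or after first dose of investigational product, as determined by" the pre-dose item being answered No or left missing. Only a Yes excludes it. Serious TEAEs and treatment-emergent device effects are defined as subsets of TEAEs.

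**The concern.** The protocol regards worsening as an adverse event in its own right, but the analysis variable knows only when a record began. Under the one-row rule, an event that predates the first injection keeps its pre-dose flag however severe it becomes on erenumab.

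The TEAE tables are the main description of tolerability. SAP 9.6.1 uses that definition for overall incidence, serious events, events leading to withdrawal of product, device effects and the by-grade summaries. A worsening missing from them cannot be restored from the event record at analysis, because the row holds first onset and worst grade but neither the date of change nor the grade at first dose.

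Constipation and hypertension are events of interest in SAP 9.6.1, and Protocol 2.3 names constipation as an adverse reaction with serious complications reported after marketing. A subject can have either at entry, so one has to ask whether these incidences are exposed too.

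**Working it through.** The plan gives no figure to reproduce. The check is to fix the length of the pre-dose window and then follow each kind of pre-dose event through the rules.

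**Window.** Screening lasts up to 21 days and may fall on the same day as the start of baseline (Protocol 4.1). Baseline lasts 28 to 35 days (8.1.2). Rescreening is ignored.
- Shortest: 0 + 28 = 28 days.
- Longest: 21 + 35 = 56 days.

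**Case 1: SAE between consent and first dose, ongoing on day 1, worse on erenumab.**
1. 8.2.3.1.1 puts it on the Events eCRF with a pre-dose onset, so the flag is Yes.
2. 11.4.4 and 11.4.5 put the worsening on that same row as a higher grade.
3. SAP 5.1.3 reads the flag. The event is not a TEAE, so it is not a serious TEAE, a TEAE leading to withdrawal, a treatment-emergent device effect or an entry in the by-grade tables.

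Result: excluded by the rules as written.

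**Case 2: non-serious event that begins before dosing and becomes serious on treatment.**
1. No pre-dose row is required.
2. When it is reported as an SAE, the Figure 11-1 completion instructions say: "Enter date the adverse event first started (not the date on which the event met serious criteria) rather than the date of diagnosis". That gives a pre-dose start.
3. Figure 11-1 is a contingency form for SAEs, used when electronic data capture is unavailable or closed. It is only indirect evidence of how onset is entered in the ordinary system.

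Result: excluded if the site treats it as the same event and dates it from first onset.

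**Case 3: non-serious pre-existing condition that worsens but stays non-serious.**
1. 8.2.1.3 places the condition in medical history, which includes a gastro-intestinal eCRF, with current severity if unresolved. No pre-dose Events row need exist.
2. 11.4.1 makes the exacerbation an adverse event. It occurs after first dose, so 8.2.3.1.1 requires it to be reported.
3. If onset is the date of worsening and the flag is No or missing, it is a TEAE. If the flag is answered by the first start of the condition, it is Yes and the event is not a TEAE.

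Result: the first reading is the natural one, but no section states the onset date or flag value, so the outcome depends on the site.

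**Which tables are affected.** In SAP 9.6.1 the overall, serious, withdrawal, device-effect and by-grade tables are labelled treatment-emergent. The treatment-related, treatment-related serious, fatal and event-of-interest tables are not. SAP 5.4.3 limits safety summaries to the period from study day 1 to end of study, without saying how a row with pre-dose onset is treated. Whether Cases 1 to 3 reach those tables is not stated.

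**The case against.** **The ordinary route works.** Non-serious conditions sit in medical history, their exacerbation is itself an adverse event, and the one-row rule in 11.4.4 concerns an adverse event between its onset and its resolution. A stable pre-existing condition is not yet one. On this reading Case 3 gives a TEAE. This stands, and it confines the definite loss to Case 1. A reader might infer that constipation and hypertension are systematically understated. The documents do not support that. It would need sites to answer the flag by first start of the condition, and the event-of-interest tables to be built on the TEAE flag. Neither is stated.

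**Case 1 is rare.** The SAE must be unresolved on day 1, the subject must still pass the day 1 eligibility check (including exclusion 205), and the same event must then worsen. This also stands. A reader might attach a count by assuming an SAE rate of 1% to 3% per 168 days: 1400 × 1% × 28/168 = 2.3, and 1400 × 3% × 56/168 = 14. That counts every assumed pre-dose SAE, not those lost. Assuming further that 10% persist and 10% of those worsen gives 2.3 × 0.01 = 0.02 to 14 × 0.01 = 0.14 subjects. At 30% and 30% it is 2.3 × 0.09 = 0.2 to 14 × 0.09 = 1.3. None of these rates is in the documents. The sums suggest a small number and are not an estimate.

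**Low stakes.** The study has one open-label arm of an approved product and no listed safety endpoint. SAEs and their updates go to the sponsor within 24 hours whatever their TEAE status. So expedited reporting loses nothing; the gap is in tabulation.

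**Other guidance may cover it.** eCRF completion instructions outside these documents might settle the point. That cannot be checked here.

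What does not stand is treating the unlabelled tables as a safeguard: SAP 9.6.1 and 5.4.3 do not say that rows with pre-dose onset enter them.

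**Conclusion.** The point holds in two parts of different strength. For an SAE recorded before first dose, ongoing on day 1 and worse on erenumab, exclusion from the TEAE and serious TEAE tables follows directly from Protocol 11.4.4 and 11.4.5 with SAP 5.1.3. Few subjects are likely to be affected, and no count can be derived because the documents give no rate of such events.

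For non-serious pre-existing conditions the documents are incomplete rather than wrong. Loss occurs only if a site answers the flag by the condition's first start. Constipation and hypertension as events of interest are affected only then, and only if those tables use the TEAE flag.

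The primary genetic analysis is untouched. The gap is still worth closing, because the remedy is small and the event record keeps nothing from which the worsening could later be rebuilt.

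**What to change.** **Protocol 11.4.4.** State that an event or condition present before first dose that worsens after it is entered as a new event, with onset equal to the date of worsening and the pre-dose flag answered No. Keep the one-row rule for events that start after first dose.

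**Protocol 11.4.5.** Add a matching exception to the instruction that new information goes on the record already completed. Otherwise the two sections conflict.

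**SAP 5.1.3.** Define a TEAE as an event starting, or worsening in CTCAE grade, on or after first dose, as captured by that new record. The SAP clause cannot work alone, because one row at worst grade has no date of worsening. The new record supplies it.

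**SAP 9.6.1.** State that the event-of-interest, treatment-related and fatal tables use the same definition.

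**Cost.** A few sentences in the two documents, aligned eCRF completion instructions, a few more eCRF rows and slightly higher TEAE counts. Subject incidence in SAP 5.6 counts a given event once per subject, so the extra row does not inflate incidence by double counting.
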